## **PROTOCOL SYNOPSIS**

Study Title	A Phase I, Randomized, Double-Blind, Placebo-Controlled, Single and Multiple Ascending Intravenous Dose Study to Assess the Safety, Tolerability, Pharmacokinetics, Pharmacodynamics and Immunogenicity of ARGX-113 in Healthy Males and Female Subjects of Non-Child Bearing Potential		
Product	ARGX-113	Clinical Phase	I
Protocol Number	ARGX-113-1501	Indication	Autoimmune Disorders
Eudract Number	2015-003549-24		

Sponsor	arGEN-X
Sponsor Representative	[name] Chief Development Officer [name]
Clinical Center(s)	Clinical Pharmacology Unit Antwerpen SGS Life Science Services [name]

### **Objectives:**

The primary objectives of this study are:

- To evaluate the safety and tolerability of a single ascending intravenous doses of ARGX-113 in healthy male subjects and female subjects of non-child bearing potential, compared to placebo (Part 1).
- To evaluate the safety and tolerability of multiple ascending intravenous doses of ARGX-113 in healthy male subjects and female subjects of non-child bearing potential, compared to placebo (Part 2).

The secondary objectives are:

- To determine the pharmacokinetics (PK) of single and multiple ascending doses of ARGX-113 given intravenously to healthy subjects.
- To determine the pharmacodynamic (PD) and immunogenicity effects of single and multiple ascending intravenous doses of ARGX-113.

### **Overview of Study Design:**

This study is a First-in-Human, Phase I, randomized, double-blind, placebo-controlled, single-center study evaluating single (SAD) and multiple (MAD) ascending intravenous (IV) doses of ARGX-113 in healthy subjects. The study will consist of 2 parts.

Up to 68 healthy male subjects or healthy female subjects of non-childbearing potential will be selected according to the inclusion and exclusion criteria, i.e., up to 36 subjects in the SAD study (Part 1) and up to 32 subjects in the MAD study (Part 2). The SAD study will contain up to 6 cohorts of 6 subjects each, with the 6th cohort being optional (to be added if no plateau in IgG reduction is reached and if there are no safety issues with the prior dose level). The MAD study will contain up to 4 cohorts of 8 subjects each.

ARGX-113 or placebo will be administered intravenously by an infusion over 2h. A staggered approach will be observed within all dose levels. For the SAD study, for each cohort, 2 sentinel subjects will be dosed followed by 4 subjects 24h later. For the MAD study, dosing will be done in 2 subgroups, 4 subjects in each subgroup. This will apply to all MAD cohorts (8 subgroups in total). An interval of at least 14 days between dosing of the first subject of each SAD and MAD dose level will be observed.

A schematic overview of the study design for Part 1 and Part 2 is presented below:

**Part 1: SAD**

Cohort	N	Dose	Drug administration
1a	1:1	0.2 mg/kg	ARGX-113 or placebo x 1 day
1b	3:1	0.2 mg/kg	ARGX-113 or placebo x 1 day
2a	1:1	2.0 mg/kg	ARGX-113 or placebo x 1 day
2b	3:1	2.0 mg/kg	ARGX-113 or placebo x 1 day
3a	1:1	10 mg/kg	ARGX-113 or placebo x 1 day
3b	3:1	10 mg/kg	ARGX-113 or placebo x 1 day
4a	1:1	25 mg/kg	ARGX-113 or placebo x 1 day
4b	3:1	25 mg/kg	ARGX-113 or placebo x 1 day
5a	1:1	50 mg/kg	ARGX-113 or placebo x 1 day
5b	3:1	50 mg/kg	ARGX-113 or placebo x 1 day
6a 	1:1	TBD	ARGX-113 or placebo x 1 day
6b 	3:1	TBD	ARGX-113 or placebo x 1 day

The a-group refers to the sentinel subjects and the b-group refers to the remainder of the subjects in the cohort. Two sentinel subjects will be dosed, followed by 4 subjects 24h later. An interval of at least 14 days between dosing of the first subject of each SAD dose level will be observed.

active:placebo

Doses are based on weight at Day -1. These doses may be adapted according to the safety, PK and PD data obtained during the study.

Optional cohort, to be conducted as needed. Dose level to be determined (TBD).

**Part 2: MAD**

Cohort	N	Dose	Drug administration
7	6:2	10 mg/kg	ARGX-113 or placebo every 4 days on 6 occasions
8	6:2	25 mg/kg	ARGX-113 or placebo every 7 days on 4 occasions
9	6:2	Either 10 mg/kg 	ARGX-113 or placebo every 7 days on 4 occasions
		Or 25 mg/kg 	ARGX-113 or placebo every 4 days on 6 occasions
10	6:2	25 mg/kg	ARGX-113 or placebo every 7 days on 4 occasions

An interval of at least 14 days between dosing of the first subject of each MAD dose level will be observed.

active:placebo

Doses are based on weight at Day -1. Starting dose and dosing interval to be confirmed following SAD study. The doses administered for the Part 2 MAD study were determined following review of the blinded safety, PK and PD data (as available) from the Part 1 SAD study and are based on the lowest observed IgG measurement (IgG nadir) and time to IgG nadir (IgG tnadir).

Dose and dosing schedule will be chosen based on blinded results obtained from Cohorts 7 and 8. After dosing was stopped in Cohort 8, it was decided to dose 10 mg/kg every 7 days in Cohort 9. Per amendment 4, an additional Cohort 10 was added.

**Study Population:**

Healthy male subjects and healthy female subjects of non-child bearing potential.

In total up to 68 subjects are planned to be enrolled.

**Part 1 (SAD):**

Up to 30 subjects, with the potential for 6 additional subjects.

**Part 2 (MAD):**

Up to 32 subjects.

**Eligibility Criteria:****Inclusion Criteria:**

Subjects meeting all of the following criteria are eligible to participate in this study:

1. Willingness and ability to understand the purpose and risks of the study and provide signed and dated informed consent prior to any procedures and be available for all study visits.
2. Male or female of non-child bearing potential, between 18-55 years of age, inclusive, on the day of signing the Informed Consent Form (ICF).
3. Body mass index (BMI) between 18-30 kg/m^2, inclusive with a weight of at least 50 kg and no more than 100 kg.

- 
4. Female subjects must have a negative blood pregnancy test at screening and a negative urine pregnancy test at Day -1.
  5. Female subjects who are postmenopausal or surgically sterile (having had a hysterectomy, bilateral oophorectomy, or tubal ligation). Determination of serum follicle-stimulating hormone (FSH) will be done with FSH levels > 35 mIU/mL being confirmative for menopause. For hysterectomy and tubal ligation, documented confirmation will be requested.
  6. Non-vasectomized male subjects having a female partner of childbearing potential must agree to the use of an effective method of contraception until 90 days after the last administration of study drug.
  7. Male subjects have to agree not to donate sperm until 90 days after the last administration of study drug.
  8. Judged by the investigator to be in good health based upon the results of a medical history, physical examination, vital signs, 12-lead electrocardiogram (ECG), and laboratory findings.
  9. Discontinuation of all medications (including over-the-counter and/or prescription medication, dietary supplements, nutraceuticals, vitamins and/or herbal supplements such as Ginkgo biloba or Saint John's wort), except occasional paracetamol use (maximum dose of 2 g/day and maximum of 10 g/2 weeks), at least 2 weeks prior to the first study drug administration. In addition, subjects must agree to the prohibitions and restrictions for this study.
  10. Non-smokers, and not using any nicotine-containing products. A non-smoker is defined as an individual who has abstained from smoking for at least 1 year prior to the screening.
  11. Negative urine drug screen (amphetamines, barbiturates, benzodiazepines, cannabis, cocaine, opiates, methadone, and tricyclic antidepressants) at screening and Day -1.
  12. Negative alcohol breath test at screening and Day-1.

Note: A retest can be done in case of an out of range clinical laboratory test value that will determine a subject's eligibility. This retest should preferably be done at an unscheduled visit. The result of the retest will be considered for subject eligibility. If the retest is outside normal reference ranges, the subject may be included only if the investigator judges the abnormalities to be not clinically significant.

Exclusion Criteria:

Subjects meeting any of the following criteria are excluded from participation in this study:

1. Known hypersensitivity to study drug ingredients or a significant allergic reaction to any drug as determined by the investigator, such as anaphylaxis requiring hospitalization.
  2. Positive serology for hepatitis B virus surface antigen (HBsAg) or hepatitis C virus (HCV) or any history of hepatitis from any cause with the exception of hepatitis A.
  3. History of or a current immunosuppressive condition (e.g., human immunodeficiency virus [HIV] infection).
  4. History of or evidence of active or latent or inadequately treated infection with Mycobacterium tuberculosis (TB) diagnosed by a positive QuantiFERON® TB-Gold In Tube test or a positive tuberculin skin test ("Mantoux") in case of a weak positive QuantiFERON® TB-Gold In Tube test.
  5. Subjects with known clinically relevant immunological disorders.
  6. History of severe allergic or anaphylactic reactions.
  7. Symptoms of clinically significant illness in the 3 months before the initial study drug administration.
  8. Presence or having sequelae of gastrointestinal, liver, kidney or other conditions known to interfere with the absorption, distribution, metabolism, or excretion of drugs.
  9. History of malignancy within the past 5 years (except for basal cell carcinoma of the skin that has been treated with no evidence of recurrence).
  10. Clinically relevant abnormalities detected on ECG regarding either rhythm or conduction (e.g., QTcF > 450 ms [male subjects] or >470 [female subjects], or a known long QT syndrome). A first degree heart block or sinus arrhythmia will not be considered as a significant abnormality.
  11. Clinically relevant abnormalities detected on vital signs
  12. Significant blood loss (including blood donation [> 500 mL]), or had a transfusion of any blood product within 12 weeks prior to the initial study drug administration or plan one within 4 weeks after the end of the study.
  13. Treatment with any drug known to have a well-defined potential for toxicity to a major organ in the last 3 months preceding the initial study drug administration.
  14. The subject has a history of consuming more than 21 (14 for females) units of alcoholic beverages per week or has a history of alcoholism or drug/chemical/substance abuse within past 2 years prior to
-

---

screening (Note: one unit = 330 mL of beer, 110 mL of wine or 28 mL of spirits). Consumption of a large quantity of coffee, tea (> 6 cups per day) or equivalent.

15. Administration of an injectable drug within 30 days prior to the initial study drug administration.
  16. Concurrent participation, or participation within 8 weeks prior to the initial study drug administration in a drug/device or biologic investigational research study, or participation within 15 weeks prior to initial study drug administration in an investigational research study with biologic response modifier administration.
  17. Administration of a vaccine within 60 days prior to initial study drug administration.
  18. Administration of any systemic immunosuppressant agent within 6 months prior to initial study drug administration.
  19. Administration of any systemic steroid within 2 months prior to initial study drug administration;
  20. Use of a prohibited therapy within 14 days prior to initial study drug administration.
  21. Investigator or any sub-investigator, research assistant, pharmacist, study coordinator, or other staff or relative thereof who is directly involved in the conduct of the study.
  22. Any condition or circumstances that in the opinion of the investigator may make a subject unlikely or unable to complete the study or comply with study procedures and requirements.
  23. Pregnant or lactating women or women of childbearing potential.
  24. Unsuitable vein for infusion and/or blood sampling.
- 

**Test Product, Dose, Mode of Administration:**

- ARGX-113 is formulated as a sterile colorless, clear liquid for IV injection.
- The placebo will be provided as a sterile colorless, clear liquid for IV injection with the same formulation without the active ingredient ARGX-113.

ARGX-113/placebo will be administered according to the dosing schedules presented in the schematic overview of the study design.

---

**Study/Treatment Duration:**

Part 1 (SAD):

- The study consists of a screening phase (within up to 28 days before the first administration of study drug [ARGX-113 or placebo]), 1 confinement visit (Days -1 to 5), and 4 additional visits to the clinic. The total study length (per subject) will be up to 57 days; which includes the screening phase.

Part 2 (MAD):

- The study consists of a screening phase (within up to 28 days before the first administration of [ARGX-113 or placebo]), 1 confinement visit (Days -1 to 25), and up to 8 additional visits to the clinic. The total study length (per subject) will be up to 107 days; which includes the screening phase.
- 

**Criteria for Evaluation:**

Safety

- Safety signals will be assessed to determine dose escalation. Blinded safety data review meetings (Safety Committee), consisting of (but not limited to) the sponsor's Medical Monitor and the Principal Investigator will be conducted after each cohort to confirm the decision to move forward with each dose escalation.
- If safety signals are detected, including observed toxicities and/or based on the available pharmacodynamic (PD) effect, the Safety Committee can advise that the dose in the following cohort can be repeated, replaced with an intermediate dose, or decreased (Part 1).
- The decision to repeat, decrease, increase, or select an intermediate dose will be made upon satisfactory review of blinded safety data (up to at least Day 5 for Part 1: SAD and up to at least 5 days post last dose for Part 2: MAD) in at least 5 subjects from the preceding dose level, as well as blinded PK and PD data obtained on an ongoing basis as available, by the Safety Committee.

Pharmacokinetic

Individual subject plasma ARGX-113 concentrations will be used to derive PK parameters using a non-compartmental method.

The following PK parameters will be estimated, where appropriate:  $C_{max}$ ,  $t_{max}$ ,  $C_{72h}$  ( $C_{168h}$ ),  $AUC_{0-t}$ ,  $AUC_{0-72h}$  ( $AUC_{0-168h}$ ),  $AUC_{inf}$ ,  $t_{1/2,\lambda,z}$ ,  $CL$ , and  $V_z$ . Cumulative amount excreted ( $A_e$ ) in urine for each collection interval and in total will be calculated in absolute and % of administered dose values.  $CL_R$  and  $CL_{CR}$  (to check urine collection compliance) will also be presented. In addition, after multiple dose administrations,  $R_{ac}$  will be calculated.

Other PK parameters may be calculated as appropriate.

---

---

Dose normalized parameters ( $C_{\max}/\text{dose}$ ,  $C_{72\text{h}}/\text{dose}$ ,  $C_{168\text{h}}/\text{dose}$ ,  $\text{AUCs}/\text{dose}$ ,  $\text{Ae}\%$ ) will be assessed. Additional PK parameters may be calculated as appropriate.

Creatinine analysis will be performed in urine to check urine collection compliance. Creatinine clearance ( $\text{CL}_{\text{CR}}$ ) will be calculated for each fraction.

#### Pharmacodynamics

Pharmacodynamic assessments will be conducted for the SAD and MAD studies to measure for the total immunoglobulin G (IgG), IgG subtype (IgG 1, IgG 2, IgG 3, and IgG 4), IgA, IgD, IgE and IgM levels.

The PD effect will be measured by endogenous immunoglobulin concentration versus baseline change (in %). The following parameters will be calculated, where appropriate, from individual data of total IgG, IgG subtypes (1, 2, 3, and 4), IgA, IgD, IgE, IgM change from baseline:  $E_{\max}$ ,  $t_{E_{\max}}$ , and AUEC.

Unlike total IgG and IgG subtype levels, no changes in IgA, IgD, IgE, IgM levels are to be expected based on FcRn biology and pre-clinical data. As such, the abovementioned parameters will only be calculated for these types of immunoglobulins if a PD effect is observed.

The relationship between ARGX-113 concentration and total IgG or IgG subtypes 1, 2, 3, and 4, change from baseline values will be graphically presented. If appropriate, graphical relationship between main PK and PD parameters will also be assessed.

The PK/PD relationship will be assessed graphically.

#### Immunogenicity

Individual plasma titer of anti-drug antibodies (ADA) directed against ARGX-113 will be measured before first administration of ARGX-113 and at selected time points following first administration of ARGX-113 (SAD) and before every administration of ARGX-113 and at selected time points following last administration of ARGX-113 (MAD).

---

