**TIME AND EVENTS SCHEDULE: PART 2: 4-DAY DOSING INTERVAL (COHORT 7)**

Time of Visit (days)	Screening a	Day -1	Days 1, 5, 9, 13 b , and 17								Day 21	Day 22	Day 23	Day 24	Day 25	Day 27	Day 30	Day 35	Day 42	Day 49 / FU Visit	Day 63 / FU Visit s,t	Day 77 / FU Visit s,t
			Hours relative to start of study drug infusion								Hours relative to start of study drug infusion											
			0h c	2h d	4h	8h	12h	24h	48h	72h	0h	24h	48h	72h	96h	144h	216h	336h	504h	672h	1008h	1344h
Informed consent e	X																					
In-/exclusion criteria	X	X																				
Medical history/ concomitant diseases	X																					
Demographic data	X																					
Physical examination	X f	X f	X h							X h	X			X		X			X	X	X	
Vital signs g	X	X	X h	X	X	X	X	X	X	X h,i	X	X	X	X	X		X	X	X u		X	
Single 12-lead ECG	X	X	X h	X	X	X	X	X	X	X h,i	X	X	X	X	X		X	X	X u		X	
Clinical laboratory tests j	X		X h					X		X h	X		X		X	X	X	X	X	X	X	
Serum albumin determination			X h			X		X		X h	X	X	X	X	X	X	X	X	X	X	X	
Lymphocyte typing: B, T subset and NK cells	X		X h					X		X h	X			X		X	X		X	X	X	
Urinalysis	X		X h					X		X h	X		X		X	X	X	X	X	X	X	
Pharmacokinetics: Blood			X h	X		X		X	X	X h,i	X	X	X	X	X	X	X	X	X	X	X	
Pharmacodynamics k			X h	X		X		X	X	X h,i	X	X	X	X	X	X	X	X	X	X	X	
Anti-drug antibodies (ADA)			X h							X h			X		X		X	X	X			
Urine drug screen and alcohol breath test l	X	X																				
Pregnancy test m	X	X																	X u		X	
Virology/Bacterial screen n	X																					
Randomization			X o																			
Administration of study drug p			X								X											

Confinement		Check-in															Check-out g														
Concomitant therapies f	X																												X	X	X
Adverse events r	X																												X	X	X

- a. To take place between 1 and 28 days prior to administration of study drug.
- b. The following assessments will not be completed on Day 13: serum albumin determination, lymphocyte typing, vital signs, and ECG.

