- c. 0h represents the start of infusion of study drug.
- d. Assessments to take place immediately following study drug infusion.
- e. No study-related assessment is to be carried out before signing of the informed consent form.
- f. Includes weight, height and BMI at screening and weight only on Day -1.
- g. Blood pressure and pulse rate (supine) and oral body temperature.
- h. Assessments should be completed pre-dose on all study drug infusion days.
- i. On Day 21, assessments should follow the same postdose collection schedule (at 2h, 4h, 8h, and 12h postdose where applicable) as for Days 1, 5, 9, 13 (where applicable), and 17.
- j. Blood samples for safety assessments should be taken after an overnight fast (fasting for at least 10h) for unbiased glucose determination.
- k. Total IgG, IgG subtypes (IgG 1, IgG 2, IgG 3, and IgG 4), IgA, IgD, IgE and IgM.
- l. Urine drug screen will test for: amphetamines, barbiturates, benzodiazepines, cannabis, cocaine, opiates, methadone, and tricyclic antidepressants.
- m. For women, a serum pregnancy test at screening and urine pregnancy test at other visits will be performed.
- n. Includes HbsAg and anti-HCV antibodies, HIV antibodies and TB serology.
- o. Randomization to be completed pre-dose on Day 1 only.
- p. Study drug will be administered as an IV infusion over 2h every 4 days (96h) (i.e., on Days 1, 5, 9, 13, 17 and 21). The dosing interval for the Part 2 MAD Cohort 9 will be chosen following review of the blinded data from the Part 2 MAD Cohort 8 (see Section 3.4.2).
- q. Subjects will be released from the unit once review (clinical laboratory tests, albumin, physical examination, vital signs and ECG) has been completed of all Day 25 safety assessments.
- r. Adverse events and intake of concomitant medication(s) will be monitored continuously from informed consent signature until the last study-related activity.
- s. These visits can be planned with a window of ± 2 days.
- t. Not applicable for Cohort 9.
- u. Only applicable for Cohort 9 and for subjects in Cohort 7 who do not consent to the additional visits added in this amendment.

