## **TIME AND EVENTS SCHEDULE: PART 2: 7-DAY DOSING INTERVAL (COHORT 8, COHORT 9, AND COHORT 10)**

Time of Visit (days)	Screening a	Day -1	Days 1, 8, and 15								Day 22	Day 23	Day 24	Day 25	Day 27	Day 28	Day 31	Day 36	Day 43	Day 50 / FU Visit	Day 64 / FU Visit d,e	Day 78 / FU Visit d,e	
			Hours relative to start of study drug infusion								Hours relative to start of study drug infusion												
			0h b	2h c	4h	8h	12h	24h	72h	120h	0h	24h	48h	72h	120h	144h	216h	336h	504h	672h	1008h	1344h	
Informed consent f	X																						
In-/exclusion criteria	X	X																					
Medical history/ concomitant diseases	X																						
Demographic data	X																						
Physical examination	X g	X g	X i							X i	X			X		X			X	X	X		
Vital signs h	X	X	X i	X	X	X	X	X	X	X ij	X	X	X	X	X		X	X	X k		X		
Single 12-lead ECG	X	X	X i	X	X	X	X	X	X	X ij	X	X	X	X	X		X	X	X k		X		
Clinical laboratory tests l	X		X i					X	X	X	X i	X		X		X	X	X	X	X	X	X	
Serum albumin determination			X i					X	X	X	X i	X	X	X	X	X	X	X	X	X	X	X	
Lymphocyte typing: B, T subset and NK cells	X		X i				X		X	X i	X			X		X	X		X	X	X		
Urinalysis	X		X i				X		X	X i	X		X		X	X	X	X	X	X	X	X	
Pharmacokinetics: Blood			X i	X		X		X	X	X	X ij	X	X	X	X	X	X	X	X	X	X	X	
Pharmacodynamics m			X i	X		X		X	X	X	X ij	X	X	X	X	X	X	X	X	X	X	X	
Anti-drug antibodies (ADA)			X i								X i			X		X		X	X	X			
Urine drug screen and alcohol breath test n	X	X																					
Pregnancy test o	X	X																		X k		X	
Virology/Bacterial screen p	X																						
Randomization			X q																				
Administration of study drug r			X								X												

Confinement		Check -in																	Check -out s													
Concomitant therapies t	X																												X	X	X	
Adverse events t	X																												X	X	X	

- a. To take place between 1 and 28 days prior to administration of study drug.
- b. 0h represents the start of infusion of study drug.
- c. Assessments to take place immediately following study drug infusion.

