- d. These visits can be planned with a window of ± 2 days
- e. Not applicable for Cohort 9.
- f. No study-related assessment is to be carried out before signing of the informed consent form.
- g. Includes weight, height and BMI at screening and weight only on Day -1.
- h. Blood pressure and pulse rate (supine) and oral body temperature.
- i. Assessments should be completed pre-dose on all study drug infusion days.
- j. On Day 22, assessments should follow the same postdose collection schedule (at 2h, 4h, 8h, and 12h postdose where applicable) as for Days 1, 8, and 15.
- k. Only applicable for Cohort 9.
- l. Blood samples for safety assessments should be taken after an overnight fast (fasting for at least 10h) for unbiased glucose determination.
- m. Total IgG, IgG subtypes (IgG 1, IgG 2, IgG 3, and IgG 4), IgA, IgD, IgE and IgM.
- n. Urine drug screen will test for: amphetamines, barbiturates, benzodiazepines, cannabis, cocaine, opiates, methadone, and tricyclic antidepressants.
- o. For women, a serum pregnancy test at screening and urine pregnancy test at other visits will be performed.
- p. Includes HbsAg and anti-HCV antibodies, HIV antibodies and TB serology.
- q. Randomization to be completed pre-dose on Day 1 only.
- r. Study drug will be administered as an IV infusion over 2h every 7 days (i.e., on Days 1, 8, 15, and 22). The dosing interval for the Part 2 MAD Cohort 9 will be chosen following review of the blinded data from the Part 2 MAD Cohort 8 (see Section 3.4.2).
- s. Subjects will be released from the unit once review (clinical laboratory tests, albumin, physical examination, vital signs and ECG) has been completed of all Day 25 safety assessments.
- t. Adverse events and intake of concomitant medication(s) will be monitored continuously from informed consent signature until the last study-related activity.

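### In Part 2 the last ADA sample is at Day 49/50, but PK and PD blood is drawn at the added visits to Day 77/78, so the last 28 days of that follow-up have no antibody data

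*Protocol*

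**What the plan says.** The secondary objectives in the protocol synopsis include "To determine the pharmacodynamic (PD) and immunogenicity effects of single and multiple ascending intravenous doses of ARGX-113". Under Criteria for Evaluation, the Immunogenicity paragraph states that plasma ADA titres in the multiple-dose part are measured "before every administration of ARGX-113 and at selected time points following last administration of ARGX-113 (MAD"). It does not name the time points or say when sampling ends, so the two Part 2 Time and Events Schedules define it.

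The 4-day schedule doses "every 4 days (96h) (i.e., on Days 1, 5, 9, 13, 17 and 21"). The 7-day schedule doses "every 7 days (i.e., on Days 1, 8, 15, and 22"). Each has two late follow-up visits, on Days 63 and 77 or Days 64 and 78. Footnotes in both tables exempt Cohort 9 from them. Footnote u of the 4-day table shows that they were added by amendment and depend on consent in Cohort 7: "Only applicable for Cohort 9 and for subjects in Cohort 7 who do not consent to the additional visits added in this amendment".

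In the 7-day table the row "Anti-drug antibodies (ADA") is empty at Days 64 and 78, while the PK blood and PD rows are marked there. In the 4-day table the ADA row is empty at Days 63 and 77, while the row "Pharmacokinetics: Blood" and the PD row run on into the added visits. The text at hand gives no reason for the difference.

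**The concern.** When follow-up was lengthened, PK and PD were carried into the new visits and ADA was not. Two things are lost. First, no sample exists that could show an antibody first becoming detectable after Day 49/50. Second, late concentrations and IgG values feed the terminal half-life, AUCinf, AUEC and the PK/PD plots. An unusual late value cannot be checked against a same-day ADA result. Both losses fall on a stated secondary objective.

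**Working it through.** The protocol states no power, sample size or error rate for this point. The check is a reading of the schedule plus date arithmetic.

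**1. Reading the rows.** In the 7-day table the ADA, PK and PD rows line up with their headings as they stand. The pre-dose mark for the last dose falls under Day 22. ADA then follows at Days 25, 28, 36, 43 and 50, with Days 64 and 78 blank. PK and PD are marked at every visit from Day 22 to Day 78.

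In the 4-day table the extracted rows sit one column too far left. The mark carrying the pre-dose footnote appears under a 72 h column, but it must belong to Day 21, as footnote i confirms: "On Day 21, assessments should follow the same postdose collection schedule". Realigned, ADA falls at Day 21 pre-dose and then Days 24, 27, 35, 42 and 49, and PK and PD run to Day 77. Read without realignment, ADA would end at Day 42 and PK and PD at Day 63. ADA is blank at Days 63 and 77 either way, so the gap does not come from the text extraction. The 7-day table shows it without any correction.

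**2. Time after the last scheduled dose** = (visit day − last dosing day) × 24 h.

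| Group | Last scheduled dose | Last ADA | Last PK/PD |
|---|---|---|---|
| Part 1 | Day 1 | Day 29: 28 d = 672 h | Day 29: 28 d = 672 h |
| Cohort 7 (4-day) | Day 21 | Day 49: 28 d = 672 h | Day 77: 56 d = 1344 h |
| Cohorts 8 and 10 (7-day) | Day 22 | Day 50: 28 d = 672 h | Day 78: 56 d = 1344 h |
| Cohort 9 (7-day, no late visits) | Day 22 | Day 50: 28 d = 672 h | Day 50: 28 d = 672 h |

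The hours agree with the column headings. The intermediate late visit is 63 − 21 = 64 − 22 = 42 days = 1008 h. PK and PD are thus taken at 1008 h and 1344 h with no ADA, and this happens only where follow-up was extended.

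**3. Cohort 8.** The Part 2 dosing table says that dosing was stopped in this cohort but not after which dose. Assume that the visits stayed on their scheduled days. If the last dose given was on Day 15, Day 8 or Day 1, then Day 50 is 35, 42 or 49 days after it. The 28-day figure is safe only relative to the last scheduled dose.

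**4. Number of samples.** Cohorts 7, 8 and 10 have 8 subjects each (6 active, 2 placebo).
- All three cohorts: 3 × 8 = 24 subjects; 24 × 2 visits = 48 samples.
- Cohort 10 alone: 8 × 2 = 16 samples.
- Final visit only: 24 samples, or 8 for Cohort 10.

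These are ceilings, because some Cohort 7 subjects may have declined the late visits.

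**The case against.** The strongest reply is that nothing here is wrong on the protocol's own terms. The Immunogenicity paragraph leaves the post-dose time points open, and the schedules comply: a sample before each dose and five after the last. The objective sets no duration. That stands. A reader might infer that the schedule contradicts the immunogenicity text, but it does not.

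A reader might also infer that late-emerging antibodies in general are invisible. They are not. Sampling continues to 48 or 49 days after the first dose, and five samples cover the 28 days after the last scheduled one. Only first detection beyond that point is lost. Likewise, the match with Part 1's 28 days holds only when counted from the last dose.

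A further tempting argument is that the drug lowers IgG, that ADA are mostly IgG, and that sampling therefore stops when ADA are hardest to detect. The Pharmacodynamics section says only that total IgG and its subtypes are expected to change and that the other classes are not. It gives no antibody class for ADA, no IgG recovery time, no drug half-life, no assay drug tolerance and no time to antibody onset. The point should not rest on that mechanism.

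Nor do the documents say that a subject who seroconverts late would be reported as ADA-negative. Classification rules commonly sit in the statistical analysis plan, which is not at hand.

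Finally, a rationale may exist in protocol sections not reproduced here; the footnotes refer to a Section 3.4.2. The missing reason therefore carries little weight. None of this explains why blood is drawn at two visits for PK and PD but not for ADA.

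**Conclusion.** The point holds as a cheap, worthwhile improvement. Where the late visits apply, ADA observation ends 28 days after the last scheduled dose and PK/PD observation ends at 56, so the second half of that period has no antibody data. It affects up to 24 subjects (18 on active). Cohort 7 consent makes that a maximum, and the Cohort 8 dosing stop makes the 28 days inexact for that cohort. Cohort 9 and Part 1 are unaffected by the mismatch. The conclusion rests on the schedule tables alone. How many antibodies would be missed cannot be calculated from the protocol, and no particular rate should be implied.

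**What to change.** Mark ADA at Days 63 and 77 in the 4-day schedule and at Days 64 and 78 in the 7-day schedule, or at minimum at the final visit. Take it from the blood already drawn: the protocol measures both ADA titre and drug concentration in plasma. Apply it to every subject who still has these visits. That means Cohort 10 prospectively, and Cohorts 7 and 8 where the visits are still to come or suitable plasma has been retained. If the sponsor prefers to leave the schedule unchanged, a sentence should say why 28 days is enough for ADA when PK and PD are followed for 56.

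The cost is a schedule amendment and at most 48 assays, with up to 16 of these for Cohort 10. No visit or venepuncture is added.
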